#### **10.1.6 Data Source: Central Data Repository**

A **Central Data Repository** located on Boston Medical Center's (BMC) HIPAA compliant server (\tripdata\$) will house datasets containing PHI from REDCap, Aunt Bertha and the EHRs to be compiled, de-identified and coded for analyses.

Using the instance of SAS on BMC's I2B2 restricted use server, the EHR data will be merged with the REDCap and Aunt Bertha data using medical record number (MRN) and date of birth, and incorporating the unique study ID assigned in REDCap. Once the EHR data is merged with project data, personal identifiers, such as patient name, medical record number, full address (excluding zip code) and phone number, will be removed from the dataset and stored as a separate encrypted dataset in a dedicated secure folder on the F drive within the restricted I2B2 BMC server. An individual's study ID will be the 'crosswalk' linking this master file containing PHI to the coded analytic dataset. Access to the master file will be limited to the BEDAC and BMC staff listed on this application who will be trained in handling confidential data and will be destroyed upon study completion.

Once treatment outcomes are verified by BMC staff, date of birth and treatment dates will be transformed into analytic variables (e.g. age at diagnosis, days to first treatment, # of days on chemotherapy, days to hormone therapy, etc.), removed from the dataset and stored as a separate encrypted dataset, linked only by the crosswalk file, as described above.

For additional information regarding the data sources, process for codification and patient identifying variables see Figure 1, and Table 1.

The master file containing an individual's name and medical record number will be used to identify navigated patients to contact for interviews. The data analyst will generate a list of patient names, MRNs, and study IDs for navigated patients, stored on the tripdata\$ server. This list will only be accessed by TRIP RAs when identifying navigated patients to contact for interviews.

### **10.1.7 Data Source: Cost Surveys**

Using an annual survey of clinical site administrators and patient navigators, we will systematically assess all costs associated with the delivery of the multi-component intervention to estimate the costs that would be required to implement in other practice settings or continue the intervention in these settings at the conclusion of the study. This data collection will inform sustainability and dissemination efforts by assessing fixed and variable costs, including costs in developing the registry and Aunt Bertha platform; costs associated with training patient navigators; and costs associated with implementing the program. The surveys will collect aggregate data on the amount of time spent on discrete navigation activities and will not contain any patient-level information.

Navigators and their supervisors will be sent a blank template of the survey via a secure electronic data capture system or secure email, or delivered a printed copy during a regularly scheduled site visit. They will be instructed to complete the survey once per day over a two-week period (10 consecutive working days). At the end of each week, a research assistant will contact the navigator by secure email or phone to aid in completing the surveys and collect the paper forms, if there are any. If during the 2 week period the navigators do not interact with any TRIP participants or spend time on any TRIP activities, the process will occur again and they will be asked to fill out a cost survey for another 2 week period. The research team will send the completed surveys to the TRIP cost analyst, based at the Boston University Medical Campus, via secure email for analysis. Paper surveys will be scanned and stored in the secure Box.com folder, and paper copies shredded immediately afterward.

### **10.1.8 Data Source: Observations**

To understand patient navigators' adherence to navigation guidelines, we will conduct observations of all TRIP Patient Navigators across participating sites at 12 months of the intervention period. We expect to observe approximately 8-12 navigators, knowing that staffing changes may alter the number of TRIP navigators over time. Observers will be IRB-approved study personnel. They will use implementation science frameworks and methods to examine the barriers and facilitators to implementation, as well as the Patient Navigators' degree of fidelity,

to the TRIP intervention protocol. Trained research staff will complete a minimum of two 4-hour observations per navigator and data will be recorded on an observation tool (**Appendix V**) to take field notes, and check off when activities from the 11 Step Navigation Guidelines are completed. The observer will begin a new written observation sheet every 15 minutes.

*Pilot Observation Period:* Observers will conduct a 2-hour pilot observation prior to formal observation activities. The pilot will ensure observers are recording observations and writing observation summaries in alignment with study protocol. No research data will be collected.

*Formal Observation Period:* Prior to the observation, the Study Coordinator will facilitate a warm hand-off between the observer and the patient navigator via email. The Study Coordinator will send an introductory email with additional details about the observation and confirm a time for the 4-hour observation periods. Observers will meet all site-specific criteria for visitor privileges ahead of the visit date. Before the start of the observation period, the observer will review an exempt information sheet (see **Appendix XI**) with the Patient Navigator, who will have the opportunity to provide verbal consent or opt out of the observation. The observer will also provide the business card of the PI, [name].

During the observation period, the observer may ask probing questions to clarify patient navigator activities. Should the observer witness an in-person patient interaction or a phone call, between the navigator and the patient, the navigator will ask for the patient's permission for the observer to remain in the room using a provided script (**Appendix XII**). If the patient does not agree, the observer will leave the room until the navigator is done interacting with a patient. If the patient is comfortable with the observer's presence, the observer will remain in the room and record notes. To remain as unobtrusive as possible this portion of the observation will be an "eyes-only" experience; the observer will not ask any questions while the patient is in the room or on the phone. Research team members will make all attempts to minimize their exposure to PHI throughout the observation period. Clinical staff can ask the research team members to leave the room at any time.

Immediately after the observation, the observer will complete an observation summary (**Appendix XIII**) independently to reflect on activities witnessed during observations and document emergent themes and questions. The observation team will review the observation summary the following day. The observer will update the summary with any remaining answers or clarifying information. No patient information will be recorded.

All observation data will be stored at BMC. Paper copies of observation notes will be scanned and stored in a secure, restricted access Box.com folder. Observers will type up hand-written field notes and store electronic copies, along with observation summaries, on a secure BMC Box.com folder. Hand-written notes will then be immediately destroyed. Observation data will be uploaded into Dedoose software for analysis by the subject's unique study ID. We will use content analysis (where we conduct counts for specific activities, e.g. entering data into the EHR, and the amount of time spent on those activities) and thematic analysis to analyze the tasks and work flow observed by the research team.

### **10.1.9 Data Source: Key Informant Interviews**

12-Month Interviews: Interviews will be conducted with Key Informants approximately 12 months after each site goes live with the TRIP intervention to assess two implementation outcomes: acceptability and penetration of the TRIP protocol. These Key Informants will be the TRIP Navigators across the 6 participating sites, as well as select members of the Non-TRIP

Navigation Team identified by the TRIP Navigator or during navigator observations, such as resource specialists, nurses, social workers, and other staff involved in the navigation process (**see Appendix I for interview guide**). There are separate, tailored interview guides for the non-TRIP Navigation Team and TRIP Clinical Champions (**Appendix II and III**).

After the study information sheet (**Appendix XVII**) has been reviewed and the interview scheduled, study team personnel will arrange a time and location for the interview. The interview will be conducted preferably in person, but phone interviews will be permitted if scheduling constraints arise. Interviews will be arranged at a mutually agreeable time and private location (clinical space, research office). Prior to beginning the interview, the research team member will confirm that the participant agrees to have the conversation audio recorded. Navigator interviews will be focused on gathering their perspectives on the TRIP navigation protocol, experiences using the REDCap Registry and Aunt Bertha SDOH platform, and perceptions of TRIP in general. Non-TRIP Navigation Team interviews will focus on perceptions of the intervention, experiences with patients receiving the new standard of care, challenges encountered, and intention to continue implementing principles of TRIP after the study period. The interview will be conducted using a flexible interview guide, and participants will be provided with an opportunity at the end of the interview to ask questions or provide other information not solicited by the interviewer. Interviewees, both TRIP Navigators and non-TRIP navigation personnel, will each receive an honorarium of \$50 for their time at the time of the interview. At the conclusion of the interview, the interviewer will make field notes, reflecting on the interview context, using an interview summary (**Appendix XII**). These notes will be marked with the participant's study ID (no names or other identifying information). If the interview is cut short or interrupted for any reason, the interviewer and interviewee will identify a mutually agreeable time, by phone or in person, to complete the rest of the interview.

Audio files will be transcribed by a verified transcription service and will be managed, coded and analyzed using qualitative data management software (either Dedoose or NVivo). All interview data – audio and written transcripts – will be stored securely in a restricted-access Box.com folder.

For analysis, at least two members of the study team will independently review transcripts from each of the first 3 Navigator and Non-TRIP Navigation Team interviews to identify important concepts that emerge and create a codebook used for subsequent interviews. Then, two coders will independently code three randomly chosen cases for agreement analysis in Dedoose or NVivo. Coders will meet twice monthly to review code interpretation and to discuss new codes. Disagreements about code meanings will be resolved by consensus.

The thematic analysis will focus on the perceptions of acceptability and penetration related to implementing the TRIP standard of care. After coding is finalized and consensus has been reached, codes will be reviewed to generate cross-cutting themes within each group. Similarities and differences in the themes will be compared across groups. This will allow us to identify the extent to which TRIP is seen as acceptable or having substantial reach within the health system among different sites.

**27-Month Interviews:** Interviews will be conducted with Key Informants approximately 27 months after each site goes live with the TRIP intervention to assess four implementation outcomes: fidelity, acceptability, adoption, and penetration of the TRIP protocol. These Key Informants will

be the TRIP Navigators across the 6 participating sites, as well as their direct supervisor or program clinical champion (**see Appendix XVI for interview guide**). Key informants will be recruited by email or at a regularly scheduled TRIP meeting (e.g. clinical advisory panel, navigator network meeting, or site visit).

After the study research information sheet (**Appendix XVII**) has been reviewed and the interview scheduled, study team personnel will arrange a time and location for the interview. The interview will be conducted preferably in person, but phone interviews will be permitted if scheduling constraints arise. Interviews will be arranged at a mutually agreeable time and private location (clinical space, research office). Prior to beginning the interview, the research team member will confirm that the participant agrees to have the conversation audio recorded. Navigator interviews will be focused on gathering their perspectives on the TRIP navigation protocol, experiences using the REDCap Registry and Aunt Bertha SDOH platform, and perceptions of TRIP in general. Supervisor and clinical champion interviews will focus on perceptions of the intervention, experiences with patients receiving the new standard of care, challenges encountered, and intention to continue implementing principles of TRIP after the study period. The interview will be conducted using a semi-structured interview guide, and participants will be provided with an opportunity at the end of the interview to ask questions or provide other information not solicited by the interviewer. The interviewee will complete a demographic survey, which is included at the end of the interview. Phone interviewees will receive the demographic survey as a REDCap survey link. Interviewees will each receive an honorarium of \$50 for their time at the time of the interview. At the conclusion of the interview, the interviewer will make field notes, reflecting on the interview context, using an interview summary (**Appendix XII**). These notes will be marked with the participant's study ID (no names or other identifying information). If the interview is cut short or interrupted for any reason, the interviewer and interviewee will identify a mutually agreeable time, by phone or in person, to complete the rest of the interview.

Audio files will be transcribed by a verified transcription service and will be managed, coded and analyzed using qualitative data management software (either Dedoose or NVivo). All interview data – audio and written transcripts – will be stored securely in a restricted-access Box.com folder.

For analysis, at least two members of the study team will independently review transcripts from each of the first 3 Navigator and Supervisor/Clinical Champion interviews to identify important concepts that emerge and create a codebook used for subsequent interviews. Then, two coders will independently code three randomly chosen cases for agreement analysis in Dedoose or NVivo. Coders will meet two to four times monthly to review code interpretation and to discuss new codes. Disagreements about code meanings will be resolved by consensus.

The thematic analysis will focus on the perceptions of fidelity, adoption, acceptability, and penetration related to implementing the TRIP standard of care. After coding is finalized and consensus has been reached, codes will be reviewed to generate cross-cutting themes within each group. Similarities and differences in the themes will be compared across groups. This will allow us to identify the extent to which TRIP has been incorporated into an existing site according to the protocol, is seen as acceptable, or having substantial reach within the health system among different sites.

### 10.1.10 Data Source: Patient Interviews

Interviews will be conducted with 30 patients enrolled in the study across all 6 TRIP clinical sites to assess acceptability of the TRIP protocol, a key implementation outcome. Patients will be identified through the central data repository, which contains a record of patients who were navigated by a TRIP navigator and screened for social determinants of health. Patients will be sent an opt-out letter and research information sheet (**Appendix XVIII and Appendix XX**) to their mailing address listed in the clinical site's electronic medical record. Approximately 1 week after the opt-out letter has been mailed, a researcher will call the patient at their phone number listed in the clinical site's electronic medical record or the REDCap Patient Registry to schedule an interview time. All interviews will be conducted by phone. Patients who opt out will be removed from the calling list. This calling list will be stored in a secure Box.com folder.

[figure not shown]
Prior to beginning the interview, the research team member will review the research information sheet (**Appendix XX**) with the participant and confirm that the participant agrees to have the conversation audio recorded. The interview will be conducted using a flexible interview guide (**Appendix XIX**), and participants will be provided with an opportunity at the end of the interview to ask questions or provide other information not solicited by the interviewer. Interviewees will each receive an honorarium of \$25 for their time at the time of the interview. Participants' responses will not be linked to identifiable information. Participants and interviewers will be asked to use pseudonyms during the interview.

Audio files will be transcribed by a verified transcription service and will be managed, coded and analyzed using qualitative data management software (either Dedoose or NVivo). All interview data – audio and written transcripts – will be stored securely in a restricted-access Box.com folder.

For analysis, at least two members of the study team will independently review transcripts from the first 3 interviews to identify important concepts that emerge and create a codebook used for subsequent interviews. Then, two coders will independently code three randomly chosen cases for agreement analysis in Dedoose or NVivo. Coders will meet twice monthly to review code interpretation and to discuss new codes. Disagreements about code meanings will be resolved by consensus.

The thematic analysis will focus on the perceptions of acceptability related to implementing the TRIP standard of care. After coding is finalized and consensus has been reached, codes will be reviewed to generate cross-cutting themes within each group. Similarities and differences in the themes will be compared across groups. This will allow us to identify the extent to which TRIP is seen as acceptable by patients.

**Figure 1 Data Sources and Codification Procedure**

**Table 1. Overview of Patient Identifying Elements**

Data Source	Description	Access	Purpose of data	PHI data elements
HIPAA Compliant REDCap Registry	A tool to support the daily work of Patient Navigators to manage their active caseload and share information with Navigators when they transfer their care to another institution in the TRIP program. Use of the registry is considered a standard part of the Navigator's workflow.	Patient Navigators across all 6 sites, Select members of the TRIP program team (all IRB approved and compliant)	Implementation data: will determine if the standard of care navigation protocol was administered	
 
• Intake date
 
• MRN
 
• Patient Name
 
• DOB
 
• Address
 
• Phone number
 
• Email
 
• Appointment dates
 

HIPAA Compliant Aunt Bertha Platform	A tool to support the daily work of Patient Navigators to systematically screen patients for barriers to care and identify local resources to help them overcome those barriers. Use of the platform is considered a standard part of the Navigator's workflow.	Patient Navigators across all 6 sites, Select members of the TRIP program team (all IRB approved and compliant)	Implementation data: will determine if the standard of care navigation protocol was administered	
 
• Patient Name
 
• Email
 
• Phone Number
 
• Zip Code
 
• Date Social Needs Assessment Completed
 

Electronic Health Record-Potential Patient List	Automated list of patients scheduled for breast cancer care in the coming week is generated by the Site. Another tool for Navigators to identify who needs their services. Use of the list is considered a standard part of the Navigator's workflow.	Site Specific Navigators, Select members of the TRIP program team (all IRB approved and compliant)	Implementation data: will determine if the standard of care navigation protocol was administered	
 
• MRN
 
• Zip code
 
• Patient Name
 
• Race
 
• Date of visit
 

Electronic Health Records- Identification of historical controls	Site tumor registrars will compile lists of patients who meet the TRIP eligibility criteria within the historical control period, in the form of a .csv file and securely transmit to the TRIP team via restricted-access Box.com folders or via SFTP. These lists will be used to identify historical control cases for abstraction.	Select members of the TRIP program team (all IRB approved and compliant)	Identification of historical control cases	
 
• Patient name
 
• MRN
 
• DOB
 
• Date of diagnosis
 
• ZIP code
 
• Race/ethnicity
 
• Institution of care
 
• Insurance type
 
• Preferred language
 
• Date of last contact/death
 

Electronic Health Record- Manually abstracted chart data	Clinical data from patient charts will be abstracted and entered into a REDCap database. The abstraction will be performed on site by a Research Assistant	Site Specific Navigators, Select members of the TRIP program team (all IRB approved and compliant)	Outcomes data: will provide clinical data to determine care received and if any delays in care persist after the new	
 
• MRN
 
• Patient Name
 
• DOB
 
• ZIP Code
 
• Insurance
 

Data Source	Description	Access	Purpose of data	PHI data elements
	employed by that site and overseen by the site PI.		Patient navigation standard is put in place.	
 
• Institution of Care
 
• Language
 
• Date of diagnosis
 
• Date of last contact or death
 
• Breast cancer treatment dates
 
• Hospital admission & ER visit dates
 

BMC Electronic Health Record- THRIVE social needs data	Social needs data collected via THRIVE for TRIP patients will be made available to the study team to merge with the TRIP instance of Aunt Bertha for analysis.	Select members of the TRIP program team (all IRB approved and compliant)	Implementation data: will determine if the standard of care navigation protocol was administered	
 
• Patient name
 
• DOB
 
• MRN
 
• Date social needs assessment completed
 

Electronic Health Record – Identification of navigated patients for interviews	A list of patient contact information at each clinical site will be compiled by a site RA from the electronic health record and saved in a secure Box.com folder. These lists will be used to contact patients for acceptability interviews.	Select members of the TRIP program team (all IRB approved and compliant)	Contacting patients for interviews	
 
• Patient name
 
• Mailing address
 
• Phone number
 

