### Fidelity to Intervention Protocol

The assessment of intervention fidelity will utilize existing databases developed for the intervention components, protocol adherence monitoring reports, which will be reviewed at monthly in-person PI meetings (See Table 3). As part of their routine functions, navigators utilize these systems to track and monitor their activities and keep track of individual patients. Monthly aggregate reports using these databases will be generated for each navigator and reviewed by the study team. If a navigator does not achieve high levels of performance as determined by their adherence to navigation guidelines for the program, they will receive training buffer sessions as needed. If performance deficiencies are identified across navigators in specific areas, group meetings will be held to determine if protocol modifications are needed.

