## 5.1.6 Data Sources/Collection

**(1) The Electronic Health Records (EHR) will serve as the data source for all socio-demographic and clinical covariates, as well as the primary and secondary clinical effectiveness outcomes for historical controls and intervention subjects. At Boston Medical Center the EHR will also be used to source social needs screening data from a parallel instance of Aunt Bertha called THRIVE. The THRIVE SDOH for TRIP patients will be retrieved from BUMC's Clinical Data Warehouse (CDW) and merged with the social needs screening data from the TRIP instance of Aunt Bertha by the TRIP analyst. The clinical and demographic EHR data from the 6 sites will be used in two ways: 1) to create a *potential patient list* to aid Patient Navigators in identifying potentially eligible patients with new breast cancer diagnoses (these data will be kept at the clinical site) and 2) treatment data needed for TRIP analysis (i.e., Chemotherapy regimens)**

Treatment variables will be *manually abstracted* for both historical controls and enrolled intervention subjects. Abstraction into a HIPAA compliant REDCap form will be completed by trained study personnel 16-18 months after diagnosis to ensure complete treatment information is documented through the 12 months following diagnosis. The electronic health records will also be used to obtain patient contact information (mailing address and phone number) for patient interviews assessing patient acceptability of the intervention.

- (2) **The REDCap registry and SDOH screening platforms (Aunt Bertha, THRIVE, QuickBase)** are the main sources of implementation (Fidelity) data. Each will provide measures of fidelity to the intervention protocol. Navigators utilize these systems to track and monitor their activities related to individual patients. Monthly aggregate reports will be generated for each navigator, reviewed by the study team and used for performance improvement throughout the study. Fidelity metrics include categorical assessments of navigator use of these tools, and will be linked to outcomes. The REDCap registry and SDOH screening platforms will also be used to identify navigated patients for patient acceptability interviews. Only patients who have been contacted by a TRIP patient navigator and screened for social determinants of health will be contacted for participation in interviews.

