#### **10.1.5 Data Source: Electronic Health Records**

Treatment data elements will be manually abstracted for both historical control and intervention subjects from **Electronic Health Records (EHR)** at each site. Abstraction from the EHR will be conducted by a trained Research Assistant employed by that site and overseen by the site PI. Data elements from EHR abstraction will be uploaded or entered directly into the TRIP REDCap abstraction project. For more information, see *Figure 1 Table 1*.

**Intervention patients:** Potential Patient Lists will be generated locally at each participating institution to aid Patient Navigators in identifying potentially eligible patients with new breast cancer diagnoses. Every week, Patient Navigators will receive a list of patients who meet TRIP eligibility criteria and have an upcoming appointment for the following week. These lists will be generated by the EHR via a script developed by each site's IT department or research administration group and uploaded to a secure folder on the Patient Navigator's local drive or sent locally through secure email.

**Historical Controls:** Historical controls will be identified by working with each site's tumor registrar to generate a list of all breast cancer patients during the historical time period. These data will be securely stored locally at each site, and transmitted to the TRIP study team at BMC via secure Box.com folder, SFTP, or secure email. The data will then be saved to the secure tripdata\$ folder. These data will be reviewed by the TRIP data analyst to ensure completeness and correct formatting of files, and to exclude all ineligible patients according to TRIP eligibility requirements. Then the TRIP data analyst will upload the eligible patients' data to a secure REDCap project for chart abstraction. This REDCap project will be used to store clinical data manually abstracted from each EHR, and entered by the site's Research Assistant.

Historical control datasets will include the following variables requested from each site:

- a. First Name
- b. Last Name
- c. MRN
- d. Sex
- e. Race/ethnicity
- f. Date of diagnosis
- g. Date of birth

- h. ZIP code at diagnosis
- i. Primary institution
- j. Primary payer at diagnosis
- k. Date of last contact or death

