### **10.6 Quality Assurance of Data**

To ensure reliability of data entry and collection, a 15% random sample of completed manually abstracted data elements will be reviewed by the TRIP study team to ensure outcomes and covariates were accurately abstracted and data entered. This data will be checked for quality by TRIP study personnel by accessing the Electronic Health Records on a hospital-issued device using BMC's VPN services, or viewing remotely through BMC's instance of Zoom using BMC's VPN services. Any differences identified will be documented and brought to the data manager for resolution. If the data manager cannot resolve the differences identified, they will be reviewed by the Clinical Adjudication Panel, which will meet as needed through BMC's instance of Zoom. The Clinical Adjudication Panel will be composed of a rotating membership selected

from the six site clinical advisors, the study personnel who conducted the initial abstraction and the cross-check, the project manager, and the data manager.

Quality assurance reports will be prepared by the data manager on a quarterly basis and reviewed by the Principal Investigators. The reports will inform the Principal Investigators about missing, invalid, inconsistent data on selected key variables. The statistician, in collaboration with the data manager on the project will oversee preparation of the reports. The reports will contain a summary of monthly accrual and cumulative accrual, a summary of key characteristics of the study participants, a summary of the completeness and quality of data.

Quality assurance will involve engaging in good data management activities. Procedures that include checking the integrity of data storage (facilitate in collaboration with BMC IT) and examining frequency distributions statistically (in collaboration with the BU School of Public Health) to look for data anomalies such as an excessive number of 'no response' or problems with any skip patterns included in the REDCap registry forms will be in place.

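### Navigators who deliver TRIP are listed with access to the abstracted outcome data, and the abstractor may help decide disputes over it, with no masking described: an avoidable ascertainment risk

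*Combined protocol and SAP*

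**What the plan says.** **Access.** In Table 1 of section 10.1, the row for manually abstracted chart data gives access to "Site Specific Navigators, Select members of the TRIP program team (all IRB approved and compliant"). The same row states the purpose as "Outcomes data: will provide clinical data to determine care received and if any delays in care persist after the new" navigation standard begins. Among its contents are the date of diagnosis and "Breast cancer treatment dates".

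**Abstraction.** Section 10.1.5 states: "Abstraction from the EHR will be conducted by a trained Research Assistant employed by that site and overseen by the site PI". Section 5.1.6 has treatment variables abstracted by hand "for both historical controls and enrolled intervention subjects", 16 to 18 months after diagnosis.

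**Checking and disputes.** Under section 10.6, "a 15% random sample of completed manually abstracted data elements will be reviewed by the TRIP study team". Differences go to the data manager. Those left unresolved go to a Clinical Adjudication Panel with rotating membership, drawn from the six site clinical advisors, "the study personnel who conducted the initial abstraction and the cross-check", the project manager and the data manager.

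**Verification.** Sections 10.1.6 and 10.3.4 say that dates are turned into analytic variables after BMC staff have verified treatment outcomes.

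**The concern.** Neither patients nor staff can be blinded to this intervention, so much of the protection against bias has to come from how the outcome is ascertained. Two ordinary separations are missing. The people who deliver the intervention are not kept apart from the outcome dataset. The person whose entry is in dispute is not kept apart from the decision on it.

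The primary outcome is a number of days between two charted dates. Some of those dates need judgement: which tissue sample was the first definitive diagnosis, which operation was the definitive surgery, when a hormone prescription was given. Section 9.3.1 estimates that 20% of patients use or move between more than one institution, which adds to the scope for differing readings. Section 12.3 analyses timely initiation as a proportion, so a date that moves across the cut-off changes a woman's outcome.

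**Working it through.** No figure in the plan is disputed, so the main check sets the passages side by side.

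1. **Is this the primary outcome data?** Section 4.2.1 counts days from diagnosis to first treatment. The Table 1 row holds both sets of dates and names its purpose as outcomes. Yes.

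2. **Does any task explain navigator access?** Abstraction belongs to a site research assistant. At 16 to 18 months after diagnosis it comes too late to help a navigator speed first treatment. Navigators have their own registry (section 9.3.3). Neighbouring rows (historical control lists, THRIVE data, interview contact lists) admit only selected programme staff. The potential patient list row carries the same access entry as the abstracted data, but there navigators need the list to find patients. No task for the abstracted data is stated.

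3. **What rights does access carry?** The table does not say. Section 10.1.5 has the research assistant enter the data, and no section lets navigators edit it.

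4. **Who decides a dispute?** The route is the 15% sample, then the data manager, then the panel. The abstractor and cross-checker are both eligible for the panel. Section 10.6 gives no voting or recusal rule. The voting members and quorum in section 10.4.1 are for the Data and Safety Meetings, not for this panel.

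5. **Is masking described?** Not in sections 10.1.5, 10.3.3, 10.6 or 12.3. The documents do not say that the panel is unmasked either. However, a diagnosis date read against the site's start date reveals whether a woman is a control or an intervention patient.

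**Coverage of the check.** If sampling is by record, 0.15 × 1,300 = 195 women in all. In the intervention group it is 0.15 × 667 ≈ 100, leaving about 567 outside the sample.

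**Illustration of sensitivity.** The plan's own total reproduces: 2 × 220 × 2.29 = 1,007.6, rounded up to 1,008. The planned difference is 81% − 70% = 11 points. Three assumptions are not in the documents: no true effect, 70% timely in both groups, and a fraction b of intervention women wrongly recorded as timely with no such error in controls.

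- SE = √[0.70 × 0.30 × (1/633 + 1/667) × DE], which is 0.0385 with DE = 2.29 and 0.0254 with DE = 1.
- Chance of a significant result = 1 − Φ(1.96 − b/SE) + Φ(−1.96 − b/SE).
- For b = 0.03 and DE = 2.29: b/SE = 0.78, so 0.119 + 0.003 = 12.2%.

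| b | Women of 667 | Share of 11 points | Error, DE 2.29 | Error, DE 1 |
|---|---|---|---|---|
| 1 point | 7 | 9% | 5.8% | 6.8% |
| 3 points | 20 | 27% | 12.2% | 21.8% |

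If the same number of points were misrecorded in both groups, the difference would stay at zero and there would be no inflation.

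**The case against.** The case for leaving the text alone is substantial.

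- Table 1 is an inventory of identifiers and of who may see them. Seeing a dataset is not changing it, and the research assistant makes the entries.
- Section 4.2.1.1 ties the outcome to named events, most of them objective and charted.
- The panel is a last resort. It sees only unresolved differences from the sample, its membership rotates, and the cross-checker is eligible as well as the abstractor. Both may be needed to explain what they read.
- Period-masked source text is awkward when checkers view live records by VPN or Zoom.

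Three stronger readings are tempting, and the documents do not support them.

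- **One-sided influence in favour of TRIP.** Navigators look after intervention patients, so a reader might infer this direction. But both groups share the same manual abstraction, nothing confines the check or the panel to one group, and navigators are not listed for the panel.
- **A motive from performance review.** The trigger for retraining is "If a navigator does not achieve high levels of performance as determined by their adherence to navigation guidelines for the program". That is scored from the registry and the social needs platform, not from treatment dates.
- **Errors outside the 15% sample are never looked at.** BMC staff verify treatment outcomes, to an unstated extent, and section 10.6 adds quarterly reports on missing, invalid and inconsistent key variables. A plausible but wrong date could still pass these checks, but that does not establish that it would go undetected.

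These points limit what can be claimed about bias. They do not supply a reason for navigator access, or for letting the abstractor decide a dispute over their own entry.

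**Conclusion.** The point holds as an avoidable weakness in outcome ascertainment. The plan gives those delivering the intervention access to the outcome dataset without a stated purpose or level of rights. It allows the abstractor and cross-checker to help decide unresolved differences, and it describes no masking of the panel to study period.

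The documents do not show that bias would arise, which way it would run, or how big it would be. The illustrative error rates rest on an assumed 1 to 3 point shift confined to one group and on a timeliness cut-off that sections 12.2 and 12.3 do not define. They show how sensitive the comparison would be to such a shift, not what to expect. The reason to act is that the remedy is cheap.

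**What to change.** 1. **Table 1, section 10.1.** Remove site navigators from the access entry for manually abstracted chart data. Leave their access to the health record and registry for patient care unchanged.
2. **Section 10.6.** State that the abstractor and the cross-checker may present a disputed record but do not take part in the decision. The site advisors, project manager and data manager remain available to decide.
3. **Section 10.6, where feasible.** Show the panel dates as days from an arbitrary reference day, so that the study period is not evident. First biopsy should not be the reference, because that date may itself be in dispute.

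The cost is a permissions change, a sentence or two of text, and a little preparation for each case that reaches the panel. Excluding the advisor from the patient's own hospital, or fully redacting source text, would cost more and is not needed here: the first would lose knowledge of that site's records, and the second would create a new redaction task.
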